### 3. SUMMARY OF STUDY PLAN

This is a 2:1 randomized, placebo-controlled, phase IIB oral cavity/oropharynx window of opportunity cancer chemoprevention study of ACTOplus met® XR (pioglitazone 30 mg and metformin extended release 1000 mg) daily for 10-21 days in patients undergoing planned surgery or definitive radio/chemotherapy. We plan to accrue 36 evaluable participants to this protocol. To account for an anticipated dropout rate of 8%, 39 participants will be accrued over a 12-18-month period of time. This number allows for three (3) unevaluable participants. (Note: this will start as a pilot study of the first 18 participants accrued to the protocol). Assuming a screening rate of approximately 2 participants per month and an accrual rate of 1-2 participants per month (0.5-1 per site), we expect the study to be complete within 18–24 months.

Study recruitment will occur in head and neck cancer clinics at participating institutions. Surgeons will be critical to recruitment as patients with newly diagnosed head and neck cancer will usually first meet with a surgeon.

Candidates for this protocol will be patients with newly diagnosed, histologically confirmed, stage I-IV squamous cell carcinoma or squamous cell carcinoma in situ of the oral cavity or oropharynx who will be undergoing definitive treatment (surgical, radiotherapy, chemoradiation treatment). Patients with a lesion in the oral cavity or oropharynx that is not yet biopsied, but is highly suspicious for squamous cell carcinoma, are candidates for screening but will not be randomized if the diagnosis is not pathologically confirmed. Study candidates must have a primary tumor and adjacent visually normal appearing tissue in an area that would allow for the collection of a 4 mm tissue sample from each for biomarker analysis at baseline and at the end of study.

Informed consent will be obtained prior to performance of any study procedures. The following assessments will be completed within 30 days prior to day 1 of study agent dosing. If any of these tests were conducted as part of the participant's standard medical care within the required 30 day time frame and a copy of the source document can be obtained for the study chart, those tests do not need to be repeated. If the testing is incomplete [i.e. some, but not all of the required blood tests were obtained or a

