#### 6.8.2 Randomization:

Participants who meet the eligibility criteria for the protocol will be randomized by the CLO. The PO will request randomization of a study participant by submitting (via fax or e-mail) the following documents to the CLO:

Informed Consent Form  
Eligibility Questionnaire  
Clinical safety/Eligibility lab report  
Pre-study diagnostic biopsy report  
Medical/Surgical History Worksheet

(Note: all documents submitted to the CLO must have personally identifying information deleted or completely obscured and be re-identified with the participant's PID number. Documents with visible personally identifying information will not be accepted.)

A CLO coordinator will review these documents and confirm that the participant meets the eligibility criteria and that the correct version of the ICF was signed. If eligibility is confirmed, the CLO coordinator will assign the next randomization (bottle) number in sequence for that site from a randomization list that will be pre-generated by the Statistical Center at UWCCC, as described in Section 6.4. The CLO will notify the site of the randomization number assigned to the participant. This number will correspond to the randomization number of one of the bottles of study agent issued to the site. That bottle will be requested from the site's pharmacy or other entity delegated the responsibility of study agent accountability following the site's institutional policy for requesting and dispensing study agent.

**Study agent should not be started within 48 hours following administration of an iodinated contrast agent** (commonly used in a staging CT scan). The participant's eGFR must be assessed  $\geq 48$  hours after the scan and the result must be within normal limits (see section 5.4.5) before starting study agent. To avoid missing doses of study agent (which could potentially render the participant unevaluable) if a staging test using iodinated contrast agent is planned, do not start the participant on study agent until the scan has been completed and their  $\geq 48$  hour post scan eGFR is confirmed to be within normal limits.

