### 13.2 Randomization/Stratification:

Subjects will be randomized in a 2:1 ratio between ACTOplus met® XR and placebo using permuted blocks of size 3. Each block will have a random permutation of two subjects with ACTOplus met® XR and one with placebo. To facilitate timely dispensing of the study agent, each site will receive a block of 3 bottles of study agent upon receipt of drug shipment authorization. When the site has dispensed their last kit from the block of 3, another block of three bottles will be sent until the site has reached the accrual limit assigned in their sub-award. If a site cannot complete a block in accordance with the accrual goals for the study, the site's sub-award will be amended and their remaining accrual slots will be transferred to another site. To preserve the permutation, the site must continue to make every effort to complete a block once they have received it. Due to the small sample size, there will be no stratification analysis per site.

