#### 13.4 Primary Objective, Endpoint(s), Analysis Plan:

The primary objective of this protocol is to determine whether 10-21 days of treatment with ACTOplus met® XR will result in a decrease in proliferation index (Ki-67) expression in oral cavity/oropharyngeal tumor tissue in the aerodigestive tract as compared to placebo. The primary endpoint of the study is the absolute change in proliferation index (Ki67) expression in oral cavity cancer cells from baseline to post-exposure. Baseline, post-exposure, absolute change in Ki-67, and difference in absolute change between the ACTOplus met® XR and placebo subjects will all be summarized with descriptive statistics. The primary analysis will compare the difference in absolute change in Ki-67 between the ACTOplus met® XR and placebo arms using a two-sided two-sample Student's t-test or Wilcoxon rank-sum test, as appropriate, at a significance level of 0.05.

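### Allocation is blocked 2:1 within site but the primary test has no site term, so if sites differ in mean Ki-67 change it is conservative and less powerful than a site-adjusted test

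*Combined protocol and SAP*

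**What the plan says.** **Allocation.** Section 13.2 has participants "randomized in a 2:1 ratio between ACTOplus met® XR and placebo using permuted blocks of size 3", and "each site will receive a block of 3 bottles of study agent upon receipt of drug shipment authorization". Section 6.4 describes the same shipment of whole blocks to a site, each with two active bottles and one placebo. Under 6.8.2, "the CLO coordinator will assign the next randomization (bottle) number in sequence for that site from a randomization list". Section 13.2 also asks sites to finish any block they have received, so that the permutation is preserved.

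**Analysis.** Section 13.4 compares absolute change in tumour Ki-67 between arms "using a two-sided two-sample Student's t-test or Wilcoxon rank-sum test, as appropriate, at a significance level of 0.05". Section 13.1 says the same in short form. Neither has a site term. Section 13.2 closes with "Due to the small sample size, there will be no stratification analysis per site". The only sensitivity analysis, in 13.8, concerns missing data.

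**The concern.** Blocking within site makes each completed block contribute two active participants and one placebo from the same site. Any difference between sites in mean Ki-67 change therefore drops out of the arm comparison. The unadjusted test does not use this. It leaves the between-site differences in its estimate of residual variance, so its standard error is larger than the true one whenever sites differ.

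What is at stake is efficiency. By the exact t-test, 36 evaluable participants give power just under 0.80 at the smallest effect size the plan expects, so precision that the design has already provided is worth using. The reason given in 13.2, small sample size, would have weight if a site term used up many degrees of freedom. The accrual figures suggest that it would not.

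**Working it through.** **Inputs from the plan**
- 24 active and 12 placebo evaluable; effect size 1.00, taken by the plan as the minimum expected (13.3)
- Two-sided 0.05, two-sample t-test (13.4)
- Complete 2:1 blocks of three within site (6.4, 6.8.2, 13.2)

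**Assumptions**
- Two sites. Section 3 gives 1-2 participants a month in total and 0.5-1 per site, and 1/0.5 = 2/1 = 2. Three and four sites were also run.
- ρ, the share of the variance of Ki-67 change due to site. No value is in the documents, so a range is shown.

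**1. The plan's own figure.** Equivalent equal-arm n = 1/{[1/24 + 1/12]/2} = 16. At 80% power the detectable effect is (1.960 + 0.842) × √(2/16) = 0.99. At 85% and 90% it is 1.06 and 1.15. The plan states 1.00, 1.06 and 1.15, so the table reproduces. At effect 1.00 the normal formula gives power 0.807; the exact t-test on 34 degrees of freedom gives 0.785.

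**2. Standard error.** With completed blocks, the true variance of the arm difference is (1 − ρ)σ²(1/24 + 1/12) = 0.125(1 − ρ)σ². The unadjusted test estimates about 0.125σ². The standard error is therefore too large by a factor of 1/√(1 − ρ). In simulation at ρ = 10%, the mean unadjusted standard error was 0.352 SD against a true 0.336; the site-adjusted one was 0.333.

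**3. Size.** Approximate true size is 2[1 − Φ(1.960/√(1 − ρ))], which gives 4.4%, 3.9% and 2.8% at ρ = 5%, 10% and 20%. The simulated values below agree.

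**4. Power at effect 1.00.** Two sites with six blocks each. 40,000 simulated trials per setting, except the 1% row, which used 20,000.

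| ρ | Gap between site means (2√ρ SD) | SE factor | Size, unadjusted | Power, unadjusted | Power, with site |
|---|---|---|---|---|---|
| 0 | 0 | 1.00 | 5.0% | 0.784 | 0.783 |
| 1% | 0.20 | 1.005 | 4.6-4.8% | 0.785 | 0.787 |
| 5% | 0.45 | 1.03 | 4.5% | 0.790 | 0.804 |
| 10% | 0.63 | 1.05 | 3.9% | 0.793 | 0.825 |
| 20% | 0.89 | 1.12 | 2.9% | 0.805 | 0.864 |

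The site-adjusted test held its size at about 5% in the 40,000-trial settings. The noncentral t on 33 degrees of freedom gives adjusted power 0.784, 0.804, 0.825 and 0.866 at ρ = 0, 5%, 10% and 20%. Unequal sites (eight and four blocks), three sites and four sites gave results within about half a point.

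**5. What those shares mean.** At the SD of 20-30% in 13.3, the gaps in mean change at ρ = 5%, 10% and 20% are about 9-13, 13-19 and 18-27 points. The last is close to the treatment effect being sought.

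**6. Incomplete blocks.** With 39 randomised (seven and six blocks) and three lost at random, unadjusted size was 4.7%, 4.1% and 3.1% at ρ = 5%, 10% and 20%. Power was 0.789, 0.790 and 0.805 unadjusted against 0.804, 0.823 and 0.866 with site. At ρ = 0 it was 0.783 against 0.782.

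These figures are for the t-test. The rank-sum form was not simulated.

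**The case against.** The case for leaving the plan alone is that the deciding quantity is unknown and may be close to zero. Several parts of that case stand.

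- **Site handling.** A reader might infer that site differences are likely because each institution embeds and sections its own tissue (section 3; 10.1.1.1). The endpoint is a within-participant change, with both samples processed at the same site, so a stable handling effect subtracts out. Ki-67 is stained and measured at one university (section 3; 8.1.1). The more plausible source is the mix of end-of-study samples. Under 7.6.1 these are surgical specimens for some participants and clinic punches for others, and sites may differ in that mix.
- **Validity.** A reader might infer a biased estimate or extra false positives. Neither follows: the error is in the conservative direction.
- **Power against the plan.** Unadjusted power does not fall as site variation grows; it moves from 0.784 to 0.805 in the table. The loss is relative to a better analysis, not to the stated target.
- **Confidence interval.** It is tempting to say that the trial's interval will be too wide. Section 13.4 specifies descriptive statistics and a test, and no interval.
- **Identical estimates.** Adjusted and unadjusted estimates coincide exactly only if all blocks are complete and everyone is evaluable. Section 13.3 allows for 39 randomised to obtain 36, so they will differ somewhat.
- **The sentence in 13.2.** It can be read as declining separate per-site analyses, which is reasonable at this size. On either reading, 13.4 still has no site term.

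What does not stand is sample size as a reason to omit site. With two sites the term costs one degree of freedom and about 0.1 point of power if site is irrelevant.

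**Conclusion.** The point holds as a matter of efficiency. The plan randomises by site and analyses as though it had not. The consequence is a valid but conservative primary test, and only to the extent that sites differ in mean Ki-67 change. Site adjustment gains practically nothing at a site share of 0-1%, and the larger gains in the table require sizeable gaps between sites. The documents do not support a claim that a material loss will occur.

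The conclusion rests on two sites, inferred from the accrual rates, on effect size 1.00 and on nearly complete blocks. Moderate loss of participants and three or four sites do not change it. The change is still worth making because the possible gain is several points and the possible loss about a tenth of a point.

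**What to change.** **13.4.** Make the primary comparison a linear model of absolute Ki-67 change on arm and site. If a rank test is used, specify van Elteren's site-stratified form. State in advance how any site without a completed block is pooled, recognising that a pooled group is no longer exactly a randomisation stratum. Keep the unadjusted test as a sensitivity analysis.

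**13.2.** Reword the last sentence to say only that no separate per-site analyses will be done.

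**Cost.** A wording change, to be made before unblinding, and one degree of freedom for each site beyond the first. No change to sample size, randomisation or data collection is needed.

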### 13.3 Accrual and Feasibility:

The sample size for each arm is based on comparing the absolute change in Ki67 between the ACTOplus met® XR arm and the placebo arm. The goal will be to bring to study completion a total of 36 subjects, or 24 subjects in the ACTOplus met® XR arm and 12 subjects in the placebo arm. Since our sample size is fixed at  $N=36$ , and we are randomizing at a ratio of 2:1 between ACTOplus met® XR and Placebo, our sample size/arm for the purpose of power calculations (if we had even sample sizes) would be  $n = 1/\{[1/n_E+1/n_C]/2\} = 16$ . For the power calculation,  $n = [(z_{1-\alpha/2}+Z_\beta)^2 2\sigma^2]/\Delta^2$ .

The table below shows detectable effect sizes (defined as the mean difference in the change divided by the standard deviation of the change) for various significance level  $\alpha$  and power  $1-\beta$  combinations for the primary endpoint. Based on the literature, a mean difference in the change of around 30-40% and a standard deviation of 20-30% may be reasonable to expect [61]. Given those estimates, and the sample size of 36, the minimum effect size we would expect would be at least 1.00; we would be able to detect the effect size of 1.00-1.15 with power 0.80-0.90 for a two-sided level 0.05 Student's t-test.

$\alpha \setminus 1-\beta$	0.80	0.85	0.90
0.05	1.00	1.06	1.15
0.10	0.88	0.95	1.04

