**End of study tissue sample collection:**

- If surgical excision will be the patient's first line treatment, the end of study tissue samples for biomarker analysis will be collected in conjunction with that surgery. If, for any reason, the patient's surgery is delayed beyond Day 26, the end of study tissue samples may be collected in the outpatient clinic setting.
- If the patient's first line of treatment will not be surgical excision, the end of study tissue samples for biomarker analysis will be collected in the outpatient clinic setting prior to initiation of the non-surgical treatment.

4.1.3 Participant is able to complete a minimum of 10 days of study agent dosing prior to initiation of definitive treatment for their cancer.

4.1.4 Participant is scheduled for an end of study biopsy within 22 days of starting study agent and within 52 days of their study screening visit. (If the participant is scheduled for surgical excision of the tumor and the surgery is delayed for any reason after the participant has started taking the study agent, study agent dosing may be extended up to a maximum of 25 days without compromising the evaluability of the end of study biomarkers).

4.1.5 Age  $\geq$  18 years (ACTOplus Met® XR is not recommended for use in pediatric patients)

4.1.6 ECOG performance status = 0 or 1.

4.1.7 Life expectancy is  $>$  6 months.

4.1.8 Body mass index (BMI) is  $\geq$  18.5.

4.1.9 Participant has normal organ and marrow function as defined below:

Hemoglobin	$\geq$ 10 g/dl
White blood cells	$\geq$ 3,000/microliter
Platelets	$\geq$ 100,000/microliter
Total bilirubin	$\leq$ 1.2 x institutional upper limit of normal *
AST (SGOT)	$\leq$ 1.2 x institutional upper limit of normal
ALT (SGPT)	$\leq$ 1.2 x institutional upper limit of normal
Glucose, serum	$<$ 200 mg/dL
eGFR	$>$ 45 mL/min (If eGFR is not included on the clinical lab report, the following calculator may be used: https://www.mdcalc.com/ckd-epi-equations-glomerular-filtration-rate-gfr . Select the equation: CKD-EPI Creatinine. The participant's gender, age, race, and serum creatinine are required to complete the calculation.)

\* With the exception of candidates with a diagnosis of Gilbert's disease in which case the total bilirubin may extend up to 1.5 x institutional upper limit of normal.

4.1.10 Participant is able to swallow a tablet whole.

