2	
 
No modification unless the A.E. is unacceptable to the participant or the physician feels it is in the participant's best interest medically.
 
If the A.E. may be related to dose timing, asses how the participant is dosing their study agent and if taking it at a different time of day or with a more substantial meal might help.
 
If dose modification is necessary because taking the agent with a more substantial meal did not improved the event and the participant finds it unacceptable or the physician feels it is in the participant's best interest medically, the participant may be instructed to take the study agent every other day.
 
If none of these measures is successful and the A.E. is unacceptable to the participant or the physician feels it is in the participant's best interest medically, study agent should be discontinued. However, the participant, if willing, should still be followed per the protocol schedule of events and have all study procedures conducted
 
	
 
If the A.E. may be related to dose timing, asses how the participant is dosing their study agent and if taking it at a different time of day or with a more substantial meal might help.
 
If the AE is unlikely to be related to dose timing or did not respond to taking the study agent at a different time of day or with a more substantial meal, instruct the participant to hold study agent until the AE resolves to <math>\leq</math> Grade 1 then re-start on an every-other-day dosing regimen.
 
If the AE recurs, discontinue study agent and do not re-start. However, the participant, if willing, should still be followed per the protocol schedule of events and have all study procedures conducted.
 

3	Hold study agent until consulting with the protocol's medical monitor and study chair. The medical monitor and study chair will advise whether study agent may or may not be restarted and whether a dose modification is indicated.	Discontinue study agent. Do not re-start. However, the participant, if willing, should still be followed per the protocol schedule of events and have all study procedures conducted.
4		

Hypoglycemia (The symptoms include):		
Sweating, chills and clamminess	Nervousness/shakiness/anxiety	Hunger and nausea
Irritability/impatience/confusion	Weakness/fatigue	Rapid/fast heartbeat

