## 5.7 Adherence/Compliance

5.7.1 Participants will be considered compliant for purposes of evaluability of study end points if they have taken  $\geq 80\%$  of the prescribed doses of study agent.

5.7.2 The following 4 methods will be employed to monitor participants' compliance.

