**Detectable Effect Size**

To account for the anticipated dilution of treatment effect due to 8% of the subjects being noncompliant with treatment, dropping out of the study or experiencing an unanticipated delay of surgery beyond 21 days, the sample size estimate is inflated to 39 subjects in total (26 subjects on the ACTOplus met® XR arm and 13 subjects on the placebo arm). Because of a short duration of treatment, we do not expect any random loss to follow-up.

The anticipated accrual rate is 1-2 subjects/month; therefore, our planned enrollment of 39 subjects should occur over 12-18 months.

Protocol accrual will be monitored through the NCI Division of Cancer Prevention's Accrual Quality Improvement Program (AQuIP). DCP will create an Accrual Zone Monitoring Plan for this protocol with milestones established based on the target enrollment, the projected monthly accrual rate and the projected duration of accrual. The CLO will submit accrual reports monthly to the Division of Cancer Prevention. If accrual falls below 90% of the projected goal, a corrective action plan will be required to ensure full enrollment within the stated accrual period. If accrual falls below 75% of the projected goal, an analysis of recruitment barriers and corrective recruitment action plan will be required. If accrual is falling short of the projected goal by > 75%, i.e. below 25% of the projected goal, at the quarter or half way marks, study continuation will require approval by DCP leadership.

For information regarding the study population (including gender and minority considerations), please see Section 4.3 Inclusion of Women and Minorities.

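### Section 13.3 credits a Student's t-test with power from a normal formula (t-test at 24:12: about 0.785 and 0.885), and the documents conflict on whether non-compliers are analysed, which leaves the 8% allowance with two meanings

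*Combined protocol and SAP*

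**What the plan says.** **Power.** Section 13.3 plans for 36 completers, 24 active and 12 placebo. It converts this to an equal-arm equivalent of 16 and prints a sample-size formula in z quantiles. It tabulates detectable effect sizes of 1.00, 1.06 and 1.15 (alpha 0.05) and 0.88, 0.95 and 1.04 (alpha 0.10) for power 0.80, 0.85 and 0.90. It then states that "we would be able to detect the effect size of 1.00-1.15 with power 0.80-0.90 for a two-sided level 0.05 Student's t-test". Section 13.4 names a two-sided t-test or Wilcoxon rank-sum test at 0.05 for the primary analysis.

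**The 8%.** Under the table, 13.3 gives the reason for the increase: "To account for the anticipated dilution of treatment effect due to 8% of the subjects being noncompliant with treatment, dropping out of the study". Late surgery, past 21 days, is named as a third cause, and the total becomes 39 (26 and 13). Section 3 explains the same number differently: "To account for an anticipated dropout rate of 8%, 39 participants will be accrued over a 12-18-month period of time", adding that "This number allows for three (3) unevaluable participants".

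**Who is analysed.** Section 5.7.1 reads "Participants will be considered compliant for purposes of evaluability of study end points if they have taken" at least 80% of the prescribed doses. Section 13.8 calls the primary analysis intent to treat. It leaves out those who received no agent and random dropouts, and promises a sensitivity analysis for missing data. Section 13.6 includes everyone with evaluable paired samples and lists compliance among the descriptive summaries. For participants who stop agent, 5.6 says: "However, the participant, if willing, should still be followed per the protocol schedule of events and have all study procedures conducted".

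**Delay.** Section 4.1.4 says that if surgery is delayed, "study agent dosing may be extended up to a maximum of 25 days without compromising the evaluability of the end of study biomarkers". Section 5.1 makes a participant unevaluable if biopsy or surgery cannot take place by Day 26.

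**The concern.** The power sentence names one test and uses another test's distribution. With 34 degrees of freedom the difference is small. But 13.3 treats 1.00 as the smallest effect to be expected, so it claims 0.80 there with almost nothing in hand.

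The analysis-set conflict matters more. A subject who is lost reduces the number analysed. A subject who is analysed after taking little drug leaves the number alone and shrinks the mean difference. The two need different allowances, and which one applies depends on whether the 80% rule governs the primary analysis. If it does, the randomised comparison is restricted by behaviour after randomisation. If it does not, some of the 8% dilute the effect. As written, either choice could be defended once the data are in. With 12 or 13 placebo subjects, two or three such choices are noticeable.

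**Working it through.** **Inputs.** Two-sided alpha 0.05 (13.4). 24:12 analysed, 26:13 enrolled, effect sizes 1.00 and 1.15 for power 0.80 and 0.90 (13.3). An 8% allowance, 36 to 39 (Section 3 and 13.3).

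**1. Reproduce the plan's table.** Equivalent n = 1/{[1/24 + 1/12]/2} = 16. Detectable effect = (z for 1−α/2 + z for power) × √(2/16).
- Alpha 0.05: (1.960 + 0.842) × 0.3536 = 0.991, then 1.059 and 1.146. The plan has 1.00, 1.06 and 1.15.
- Alpha 0.10: 0.879, 0.948 and 1.035. The plan has 0.88, 0.95 and 1.04.

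The table follows the normal formula to about 0.01. Normal power at 24:12 is 0.807 at 1.00 and 0.902 at 1.15.

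**2. The test that is named.** Noncentral t, df = 24 + 12 − 2 = 34, critical value 2.032, noncentrality = d/√(1/24 + 1/12) = 2.828d.

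| | Plan | t-test, 24:12 |
|---|---|---|
| Power at 1.00 | 0.80 | 0.785 |
| Power at 1.15 | 0.90 | 0.885 |
| Detectable effect, alpha 0.05 (power 0.80/0.85/0.90) | 1.00/1.06/1.15 | 1.02/1.09/1.18 |
| Detectable effect, alpha 0.10 | 0.88/0.95/1.04 | 0.90/0.97/1.06 |

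**3. The analysis-set statements side by side.**
- Restrictive: 5.7.1 (80% of doses for end-point evaluability). Two others lean the same way. Section 6.8.2 warns that missed doses might make a participant unevaluable, and 7.4.7 accepts samples up to Day 26 provided dosing continues to the day before.
- Inclusive: 13.8 (eligible and dosed, less random dropouts) and 13.6 (evaluable paired samples, compliance descriptive). Sections 5.6 and 8.3 keep collecting end-of-study data after agent is stopped, so paired samples from non-compliers can exist.
- Delay: 13.3 counts surgery beyond 21 days within the 8%, 4.1.4 says dosing to 25 days leaves evaluability intact, and 5.1 draws the line at Day 26.

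The word evaluable in 13.6 does not settle the matter, because 5.7.1 can be read into it.

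**4. What 39 covers.**
- 8% lost: 36/0.92 = 39.1. This matches Section 3; 39 × 0.92 = 35.9.
- 8% analysed with zero effect: the mean difference becomes 0.92 of its value, and N in the plan's formula scales with 1/effect², so 36/0.92² = 42.5. Thirty-nine does not cover this.

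**5. Illustrations by t-test** (power at 1.00 and 1.15).
- Three of 39 lost, no dilution: 26:10 gives 0.742 and 0.851; 25:11, 0.766 and 0.870; 24:12, 0.785 and 0.885; 23:13, 0.799 and 0.896.
- All 39 analysed (26:13), no dilution: 0.818 and 0.909.
- All 39 analysed, 2 of 26 active subjects at zero effect (assumption, by simulation): about 0.74 and 0.85. With 3 of 26: about 0.69 and 0.81.

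**The case against.** The normal approximation is conventional, the plan prints the formula it uses, and its table reproduces. The planning inputs are far looser than 1.5 points: a difference of 30-40% with an SD of 20-30% spans effect sizes from 30/30 = 1.0 to 40/20 = 2.0, and t-test power at 24:12 is already about 0.956 at 40/30. Section 13.4 also allows a Wilcoxon test. All of this stands. It makes the power part a matter of labelling and precision, although the sentence still assigns the figure to the t-test.

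On the 8%, the list in 13.3 includes dropping out, so Section 3 may simply abbreviate it, and 13.8 does remove random dropouts, which fits the loss reading in part. But absent subjects do not dilute an effect, and non-compliers who supply samples are not random dropouts. The text in 6.8.2 is a cautious scheduling note and 5.6 and 8.3 concern follow-up, so the core of the conflict is 5.7.1 against 13.6 and 13.8.

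Three stronger readings are tempting and not supported:
- A reader might infer that the stated power is reached only with all 13 placebo and at least 24 active subjects analysed. At the plan's two decimals, 23:13 also gives 0.80 and 0.90.
- A reader might infer that the arithmetic proves that loss was meant. If the 8% kept half the effect (an assumption), 36/0.96² = 39.1 as well, so the number alone cannot decide.
- A reader might take 0.74 and 0.85 as the worst case. Three active subjects at zero effect already give less, and the documents give neither the split of the 8% nor the effect left in non-compliers.

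**Conclusion.** The point holds and is minor. The power attributed to the t-test is about 1.5 points too high at the plan's own 24:12, and the detectable effects are 1.02, 1.09 and 1.18 at alpha 0.05. This rests on a normally distributed change with equal variances, as the named test assumes. It does not show that the trial is underpowered or that 39 is the wrong number.

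The material part is the unresolved status of non-compliant subjects with paired samples, together with three delay statements that do not line up. Until that is settled, the 8% cannot be read as either loss or dilution. Thirty-nine is adequate for the first reading and short for dilution at zero effect. The dilution figures are illustrations under stated assumptions, not estimates or bounds.

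**What to change.** Keep N = 39.

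(a) In 13.3, restate the power and table as t-test figures: with 24:12 analysed, about 0.785 at 1.00 and 0.885 at 1.15; detectable effects 1.02/1.09/1.18 (alpha 0.05) and 0.90/0.97/1.06 (alpha 0.10). Alternatively, label the present figures a normal approximation and give the t-test values beside them.

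(b) Before redefining the 8%, reconcile 4.1.4, 5.1, 5.7.1, 6.8.2, 7.4.7 and 13.3 with 13.6 and 13.8 in one analysis-set statement. For the primary analysis follow 13.8: eligible, dosed subjects with paired samples are analysed as randomised whatever their compliance. Use the 80% rule only for a sensitivity analysis. Bring the delay passages into agreement on who counts as evaluable, without altering any dosing rule.

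(c) Then describe the 8% to match: loss for subjects without paired samples, dilution for those analysed while non-compliant. If a dilution figure is shown, state its assumption and call it illustrative (26:13, 2 of 26 active at zero effect: about 0.74 and 0.85; 3 of 26: about 0.69 and 0.81).

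The cost is revised wording, a restated table, one sensitivity analysis and a slightly less favourable stated power. No extra participants or procedures are needed.
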